Local healthcare providers will be permitted to refer a limited number of Veterans to the intensive primary care programs (up to 10% of the program capacity). To allow usual care patients the opportunity to participate as a demonstration patient, after 12 months, high-risk Veterans in the usual care group will not be excluded from being randomly selected for an invitation to participate in the intensive management innovation.

Based on a univariate comparison, a sample size of 526 patients per evaluation arm (1052 total) will provide 90% power to detect a small effect (Cohen's $d = 0.2$) in ED visits or hospitalizations with a two-sided significance level of 0.05. The investigators estimate that at least 200 patients will have the opportunity to be invited to the intensive management program at each demonstration site over a one-year period, which will provide a sufficient sample size of 1000 patients in the innovation and 1000 in the comparison arm. Sites control the frequency and

quantity of high-risk patients identified to them each month, based on clinical and resource considerations. PIM teams are expected, however, to receive at least 200 names over 12 months, rather than all 200 at the beginning.

Interventions

Selected demonstration sites will span a variety of high-risk patient care approaches, such as a patient-centered medical home for high-risk Veterans, collaborative care model for high-risk patients, and care transitions program. Each site will propose a site-specific intervention. All proposed interventions will use population management models and determine their own approaches to stratifying patients and determining eligibility for and intensity of services. The types of services offered by each team will depend on program staff, local resources, and facility and program priorities. Each site will also develop its own criteria for when to discontinue services for patients.

Measurements

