Patient demographics, chronic conditions and other health conditions (Yoon, Scott, Phibbs, & Wagner, 2011), comorbidity score (Charlson), VHA outpatient/inpatient utilization, measures of prescription drug use and mortality will be obtained through the VHA Corporate Data Warehouse. For costs, VHA inpatient and outpatient utilization records will be linked to Managerial Cost Accounting (MCA) cost data to obtain the costs of outpatient and inpatient care. Pharmacy utilization and costs will be obtained from MCA Pharmacy files, and VHA-sponsored care is obtained from Fee Basis files. Implementation costs will be determined through micro-costing methods from site reports. Because these are administrative data, these are collected from each participant regardless if they were not offered services or if they were discontinued from the intervention.

Analysis

The investigators will conduct an intent-to-treat analysis based on patients' allocated group. The investigators plan to compare unadjusted mean utilization counts and costs for different categories of inpatient care and outpatient care and total care. The investigators will estimate the impact of PIM using regression models to obtain the differences-in-differences estimate of the change from the 12-month pre-intervention period to 12-month and 24-month post-intervention period attributable to PIM above and beyond any time trends that occurred in both groups. Our regression models will predict utilization of outpatient encounters and inpatients stays in count data models (Poisson and negative binomial regression models) including a time-varying measure of risk using the Charlson Index and patient fixed effects to account for factors fixed over time. Regression models of costs include the same predictors as the utilization models and will be conducted using ordinary least squares (OLS); sensitivity analyses will be conducted using generalized linear models (GLM) with a log link and Poisson distribution. Mortality will be compared between treatment groups with a log-rank test for equality of survivor functions.

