In other sensitivity analyses, the investigators plan to conduct regression models with patient random effects and covariates for patients' age, gender, race/ethnicity, marital status, means test, service connection, homelessness, Charlson Index, and site. The investigators will also measure the treatment effect on the treated by conducting regression analysis using instrumental variables to examine whether more PIM encounters were related to cost and utilization impacts by using randomization to PIM as an instrument for number of PIM encounters. Instrumental Variable models will use the two-staged least squares estimator.

Other Outcome Measures

Functional Status, Quality of life, Symptom Burden

Standardized assessments of symptom burden (mental health and physical health), quality of life, and functional status (physical, social, and mental) will be based on patient-reported outcomes measurement information system (PROMIS) global items. These measures will be obtained only on the innovation patients and entered into the electronic medical record using a standardized assessment template available only to the demonstration staff. Some standardized assessments are available on the entire sample as part of VHA medical records (i.e., pain score, Patient Health Questionnaire (PHQ)-2 for depression) and performance measures.

Implementation Outcome/challenges

Sample selection/ recruitment

The investigators will interview PIM staff about implementation challenges and lessons. The investigators will use PIM staffing lists from the demonstration sites to compile the sampling frame. The investigators will include in the sampling frame the team leaders, team members, and program coordinators. The investigators will select all PIM team leads and program coordinators (if the site has a coordinator), and randomly select 1 of each job title/role from the PIM team members. Team members who refuse or are ineligible will be replaced by randomly selecting another person in the same job title/role, until one completed interview is obtained for each job title/role for each site. Team members will include RNs, NPs, MDs, social workers, psychologists, and intermediate care technicians. The investigators will invite 35 potential respondents by email, and follow up by telephone and using instant messaging for those who do not respond to the initial email.

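### The instrumental-variable analysis only rescales the intent-to-treat effect per encounter: it cannot test dose-response, and its on-the-treated label is unsupported at 24 months

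*Protocol*

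**What the plan says.** The main analysis is by allocation: "The investigators will conduct an intent-to-treat analysis based on patients' allocated group" (Protocol, Primary and Secondary Outcome Measures Procedures, Analysis). It estimates changes from the 12 months before PIM to 12 and 24 months after.

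Among the sensitivity analyses in the same section, the protocol adds an instrumental-variable model. Its target is to "measure the treatment effect on the treated by conducting regression analysis using instrumental variables". Its question is "to examine whether more PIM encounters were related to cost and utilization impacts". Its instrument and exposure are set "by using randomization to PIM as an instrument for number of PIM encounters", and "Instrumental Variable models will use the two-staged least squares estimator". No second instrument is named, and neither a constant effect per encounter nor an exclusion restriction is stated.

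Two other provisions bear on this. Under Sample, after 12 months "high-risk Veterans in the usual care group will not be excluded from being randomly selected" for an invitation to PIM. The same section lets local providers refer some Veterans to the programs, up to 10% of capacity, without saying whether randomized usual-care patients may be among them.

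**The concern.** The sentence fixes an estimand, a question, an instrument, an exposure and an estimator, and these do not fit together.

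- An effect on the treated is a change per treated patient. The coefficient of an encounter count is a change per encounter.
- Whether more encounters matter is a question about the shape of the effect over the count. One two-arm allocation indicator identifies one contrast, which carries no information about shape.
- An on-the-treated reading rests on usual-care patients not receiving PIM. The protocol opens PIM to them after 12 months and still estimates effects at 24 months.

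At stake is the reading of the result. A significant coefficient would be reported as a yes to the question about more encounters, for cost (the primary outcome) and for utilization, even if encounters after the first did nothing.

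**Working it through.** **Inputs.** From the protocol: 1:1 allocation, randomization as instrument, encounter count as exposure, two-stage least squares, 12- and 24-month follow-up, 1000 patients planned per arm, usual-care access after 12 months. The protocol gives no uptake, encounter or crossover figures, so those below are assumptions.

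**The plan's own figure.** None is stated for this analysis. The only computable figure, the sample size, reproduces: 2 × (1.960 + 1.282)² / 0.2² ≈ 525.5, hence 526 per arm. It does not bear on this point.

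**Step 1: what the coefficient is.** With one binary instrument and one exposure D the model is just identified. Without covariates,

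coefficient = (mean Y in innovation − mean Y in usual care) / (mean D in innovation − mean D in usual care).

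The numerator is the ITT contrast. With covariates, or on changes from baseline, both differences become adjusted differences and the structure stays the same.

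**Step 2: hand example, no usual-care receipt.** Let uptake be p, mean encounters among users m, and average effect per user τ. Then ITT = pτ, the encounter difference is pm, and the coefficient is τ/m. How τ is spread over encounters does not enter. Take p = 0.5, m = 20, τ = −$4,000:

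- ITT = 0.5 × (−4,000) = −$2,000
- encounter difference = 0.5 × 20 = 10
- coefficient = −2,000 / 10 = −$200 per encounter
- coefficient × m = −200 × 20 = −$4,000 per treated patient
- ITT / p = −2,000 / 0.5 = −$4,000 per treated patient

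These results are the same if the whole saving comes at first contact, if each encounter saves $200, or if savings shrink with each encounter to the same average. Uptake cancels: at 30%, −1,200 / 6 = −$200; at 70%, −2,800 / 14 = −$200. With m = 10 or 40 the coefficient is −$400 or −$100.

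**Step 3: simulation, no usual-care receipt.** 1000 per arm, 2000 replicates, outcome SD 1 before any PIM effect, no covariates. Uptake and encounter count both depend on underlying severity; mean encounters among the treated are about 5.9 to 7.0. Assumed effects: −0.05 per encounter (linear); −0.4 at first contact and nothing more; or −0.4 × (1 − exp(−D/2)) (saturating).

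| Uptake | Truth | Coefficient | Coefficient × mean encounters | True effect on treated | IV significant | ITT significant |
|---|---|---|---|---|---|---|
| 30% | linear | −0.050 | −0.294 | −0.295 | 50.2% | 48.1% |
| 30% | first contact | −0.069 | −0.402 | −0.400 | 76.0% | 74.5% |
| 50% | linear | −0.050 | −0.321 | −0.322 | 94.3% | 93.6% |
| 50% | saturating | −0.050 | −0.322 | −0.319 | 93.8% | 93.4% |
| 50% | first contact | −0.062 | −0.400 | −0.400 | 98.8% | 98.8% |
| 70% | linear | −0.050 | −0.349 | −0.348 | 100% | 100% |
| 70% | first contact | −0.058 | −0.400 | −0.400 | 100% | 100% |

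The IV and ITT decisions agreed in 97.9% to 100% of replicates. With no effect at all, the IV test rejected in 4.4% to 5.4%. At 50% uptake the linear and saturating truths give the same coefficient.

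**Step 4: usual-care receipt.** Let fractions p1 and p0 of the two arms receive PIM, with mean encounters m1 and m0 among recipients. If only first contact matters, the coefficient is τ(p1 − p0) / (p1·m1 − p0·m0). Multiplying by mean encounters among recipients returns τ if p0 = 0 or m0 = m1, not in general. Simulated at 50% innovation uptake, with the dose setting halved (8 to 4) for usual-care recipients:

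| Usual-care receipt | Truth | Count model, rescaled | Any-encounter model | True effect on treated |
|---|---|---|---|---|
| 10% | first contact | −0.319 | −0.402 | −0.400 |
| 20% | first contact | −0.252 | −0.404 | −0.400 |
| 10% | linear | −0.292 | −0.368 | −0.291 |
| 20% | linear | −0.273 | −0.437 | −0.273 |

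Once usual-care patients receive PIM at a different dose, neither model gives the effect on the treated under both truths.

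**The case against.** The best defence is that the coefficient is informative. It is a valid test of whether PIM has any effect, and if every encounter has the same effect it estimates that effect, even with crossover. This stands, but the protocol does not state that assumption, and the test adds almost nothing to the ITT test.

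A reader might infer that the analysis cannot give an effect on the treated at all. That goes too far. Steps 2 and 3 show that with no usual-care receipt, and no effect of allocation except through an encounter, the coefficient times mean encounters among the treated recovers it, whatever the dose shape. The protocol opens re-selection only after 12 months, so the label problem is documented for the 24-month estimate. Crossover by referral is likewise possible but not stated.

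It can also be said that a statistical analysis plan could add instruments, such as allocation by site. It could, but the protocol names only randomization. Site-specific instruments would need their own assumption of a common per-encounter effect, which is doubtful where sites set their own services and intensity (Interventions).

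Finally, a reader might infer that the result would be used to set programme intensity. No section says so. The analysis is one of the sensitivity analyses and leaves the ITT analysis untouched.

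**Conclusion.** The point holds in a limited form. As written, the analysis would answer yes to the question about more encounters whenever the ITT effect is detectable, including when only first contact matters. Its coefficient is a per-encounter average, not an effect per treated patient; in the simulations without crossover, −0.05 to −0.07 against −0.30 to −0.40. The conversion between the two is secure only while usual-care patients have no access to PIM, so the on-the-treated label is not supported at 24 months. With assumed first-contact effects and 10% to 20% usual-care receipt at a lower dose, the converted value was −0.32 to −0.25 against a true −0.40.

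The algebra does not depend on the assumed uptake, dose and crossover; the sizes do. Severity is low to moderate.

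**What to change.** 1. Delete the question about more encounters. Otherwise report the count coefficient as a rescaled ITT effect per encounter, causal per encounter only if that effect is assumed constant, with no dose-response meaning.
2. For the effect of receipt, use at least one PIM encounter within 12 months of allocation, counted in both arms, as the exposure. Report a complier average effect at 12 months, and state that it equals the effect on the treated if no usual-care patient receives PIM in that period.
3. Do not call the 24-month estimate an effect on the treated.
4. Report the share of usual-care patients who received PIM, and how many encounters they had, alongside the estimate.

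The cost is a few sentences and one recoded variable, with no new data. There are two downsides. The dose-response claim is dropped. Any receipt is also a coarse exposure that can itself be biased if usual-care patients receive PIM at a different dose (Step 4, linear rows), which is why items 2 and 4 limit the period and report usual-care receipt.

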The investigators will look at patient PIM enrollment data by utilizing central repository administrative data. The data will be electronically abstracted through the VA central repository administrative data center.

5. Functional status

Patient report of their physical, social, and mental functional status is routinely collected as part of their medical visit. The data will be abstracted through the VA central repository administrative data.

6. Quality of Life Status

Patient assessment of their quality of life collected as part of their medical care. This information will be electronically abstracted through the VA central repository administrative data center.

7. Symptom Burden

Patient assessment of mental health and physical health symptom burden is routinely collected as part of their care and documented in their medical record. This data will be electronically abstracted through the VA central repository administrative data center.

8. Implementation Outcome/ challenges

Information about implementation barriers and facilitators, feasibility, and sustainability will be obtained through two waves of key stakeholder interviews, including demonstration site staff and facility leaders

9. Primary Care Staff Job Satisfaction and Intention to Stay at the VA

The investigators will survey Primary Care Providers (PCPs) (physicians, MDs/DOs; nurse practitioners, NPs; physician assistants, PAs) and nurses (registered nurses, RNs; licensed practical nurses, LPNs; licensed vocational nurses-LVNs) at the five healthcare systems that have a PIM team. They will use both online using RedCap and paper-and-pencil versions of the survey to increase response rate. The investigators will survey Primary Care staff at baseline and one year later. The first survey was fielded December 2014 - May 2015 and again from October 2016 - January 2017). Primary Care Staff Job Satisfaction is measured by a single item "Overall, I am satisfied with my job," rated on a 5-point Likert agreement scale.

10. Primary Care Staff Intention to Stay at the VA

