With approval from site and program leadership, stakeholders will be sent an email describing the interviews and inviting them to participate. If stakeholders do not respond to the invitation email within 2-3 business days, the investigators will follow up by either phone, instant message, or additional emails. Methods of communication will be determined by available contact information and perceived individual stakeholder preferences. The investigators will make 3 follow-up contact attempts.

Instrument Development

Two qualitative team members drew on the Consolidated Framework for Implementation Research (CFIR) and chronic care model to develop the interview guides. The interviews are designed to take approximately 30 minutes, except the program lead interviews which are approximately 60 minutes. Interview guides will be refined through piloting and consultation with PIM and evaluation team clinicians.

Procedures

Interviews will be conducted by telephone. The investigators will analyze the transcripts of these interviews thematically, guided by the Consolidated Framework for Implementation Research and the Chronic Care Model.

Analysis

All interviews will be audio recorded. Audio recordings of the interviews will be transcribed in full. Summaries will be created from the transcripts, or directly from the audio recordings, using standardized templates based on the interview guides, with additional sections included for recording good quotes, emergent themes, and analyst observations. The summarized data will then be organized into Excel matrices to facilitate within and across site comparisons.

The substantive findings from these comparisons will be disseminated to the evaluation team, the PIM sites, and to VA central office via Powerpoint presentations and written reports, providing a richly detailed record of stakeholders' perceptions of the PIM pilot project and PIM program activities and providing timely and specific formative feedback that will be used to shape and improve PIM.

[Primary Care Staff Job Satisfaction and Intention to Stay at the VA.](#)

Sample

The investigators will survey all Primary Care Providers (PCPs) (physicians, MDs/DOs; nurse practitioners, NPs; physician assistants, PAs) and nurses (registered nurses, RNs; licensed practical nurses, LPNs; licensed vocational nurses-LVNs) at the five healthcare systems that have a PIM team.

Method

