The investigators will use both online using RedCap and paper-and-pen versions of the survey to increase response rate. The investigators will survey Primary Care staff at baseline and one year later. The first survey will be fielded December 2014 - May 2015 and again from October 2016 - January 2017).

Analysis

Longitudinal cohort of staff who responds to both Wave 1 and Wave 2. The investigators will use ordinary least squares regression analysis to examine associations between the independent variable measured at wave 1 and outcome variables measured at wave 2 controlling for wave 1 outcomes among staff who completed both waves. The investigators will focus on Job Satisfaction and Intention to Stay at VA as dependent variables. The investigator will adjust for provider-level covariates (type of staff, location, type of primary care team, gender, length of time at VA) and clustering of respondents within clinics assuming a random effect using robust standard errors. The investigators will use sample weighting for nonresponse based on provider characteristics in both waves and conduct multiple imputations for item-level missing data;

Difference-in-differences between Wave 1 and Wave 2: will treat Wave 1 and Wave 2 as two independent samples and use difference-in-difference regression analysis to assess differences in outcome variables between Wave 1 and Wave 2 among PIM and usual care. The investigators will focus on primary care staff experience (e.g., stress, satisfaction with help received) working with high-risk patients as dependent variables. The investigators will adjust for covariates (type of staff, location, type of primary care team, gender, length of time at VA). The investigators will use sample weighting for nonresponse based on provider characteristics in both waves.

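### The staff-experience difference-in-differences assumes independent waves, although some staff answer both (minor)

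*Protocol*

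**What the plan says.** The Sample paragraph of the staff section takes a census: "The investigators will survey all Primary Care Providers (PCPs", together with nurses, at the five systems that have a PIM team. The Method paragraph gives the timing: "The first survey will be fielded December 2014 - May 2015 and again from October 2016 - January 2017".

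The Analysis paragraphs then describe two analyses.

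- **Cohort analysis.** It uses a "Longitudinal cohort of staff who responds to both Wave 1 and Wave 2" and regresses "outcome variables measured at wave 2 controlling for wave 1 outcomes among staff who completed both waves". Its dependent variables are set out as follows: "The investigators will focus on Job Satisfaction and Intention to Stay at VA as dependent variables". It allows for clustering within clinics through a random effect and robust standard errors.
- **Difference-in-differences.** It "will treat Wave 1 and Wave 2 as two independent samples and use difference-in-difference regression analysis" to compare PIM with usual care across the waves. Its dependent variables differ: "The investigators will focus on primary care staff experience (e.g., stress, satisfaction with help received) working with high-risk patients as dependent variables". It names covariates and nonresponse weights, but no term for dependence within person or within clinic.

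**The concern.** The cohort analysis can exist only if some people answered both surveys, and nothing in the difference-in-differences paragraph removes those people. The two samples therefore share members, and one person's answers on stress or satisfaction at two times will usually be correlated. A variance calculated as if the waves were independent leaves out that covariance.

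At stake is the inference, not the estimate. If repeat respondents stay in the same exposure group, the standard error is too large and a real change in staff experience is more likely to be missed. If most of them change group, it is too small. The protocol does not say how staff are classed as PIM or usual care, so the text does not settle the direction.

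**Working it through.** The protocol gives no sample size, power, overlap or correlation for the staff survey, so there is no figure of its own to reproduce. The size of the error has to be shown over assumed ranges.

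**From the protocol.** Both waves are a census of the same five systems. The shortest gap between fielding windows is May 2015 to October 2016, 17 months; the longest is December 2014 to January 2017, 25 months. Turnover and nonresponse make the overlap partial.

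**Assumed.** *f* is the share of respondents who are in both waves, *r* the within-person correlation, and *q* the share of repeat staff who switch exposure group. Waves and groups are of equal size, and there are no clinic effects.

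**Variance.** With *n* respondents per group and wave and variance σ², the estimate is (P2 − P1) − (U2 − U1), where P and U are the PIM and usual-care means. Under independence its variance is 4σ²/n. Repeat staff who stay in their group give each same-group pair of means a covariance of f(1−q)rσ²/n, which enters with a negative sign. Switchers give each cross-group pair a covariance of fqrσ²/n, which enters with a positive sign. Each kind occurs twice and counts double in the variance. Hence

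true variance / stated variance: v = 1 − f·r·(1 − 2q)

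stated SE / true SE: k = 1/√v

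actual size of a nominal 5% test: 2[1 − Φ(1.96k)]

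power where a correct SE gives 80%: Φ(2.80 − 1.96k)

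**Worked mid-case.** With f = 0.5, r = 0.5, q = 0: v = 1 − 0.25 = 0.75; k = 1/√0.75 = 1.155; size 0.024; power about 0.70.

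| Switching q | f, r | v | k | Actual size |
|---|---|---|---|---|
| 0 | 0.3, 0.4 | 0.88 | 1.066 | 0.037 |
| 0 | 0.5, 0.5 | 0.75 | 1.155 | 0.024 |
| 0 | 0.7, 0.6 | 0.58 | 1.313 | 0.010 |
| 0.25 | 0.5, 0.5 | 0.875 | 1.069 | 0.036 |
| 0.5 | any | 1 | 1 | 0.050 |
| 1 | 0.3, 0.4 | 1.12 | 0.945 | 0.064 |
| 1 | 0.5, 0.5 | 1.25 | 0.894 | 0.080 |
| 1 | 0.7, 0.6 | 1.42 | 0.839 | 0.100 |

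In the three rows with q = 0, power is 76%, 70% and 59%.

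**Simulation under the null.** Settings: 3000 runs each, 450 respondents per wave, 30 clinics, no clinic effects, and a t reference with 29 degrees of freedom for the clinic-clustered tests. Rejection rates:

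| f, r, q | Independence | Clustered on staff | Clustered on clinic |
|---|---|---|---|
| 0.5, 0.5, 0 | 0.029 | 0.055 | 0.056 |
| 0.5, 0.5, 0.5 | 0.049 | 0.050 | 0.050 |
| 0.5, 0.5, 1 | 0.079 | 0.055 | 0.054 |
| 0.7, 0.6, 0 | 0.009 | 0.048 | 0.051 |
| 0.7, 0.6, 1 | 0.106 | 0.055 | 0.055 |

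With f = r = 0.5, 30% of staff changing clinic and exposure set by clinic, the independence analysis rejected in 0.029 of runs and two-way clustering on staff and clinic in 0.050. Clustering brings the test to about 5% whichever way the error runs.

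**The case against.** The best defence is that the phrase announces a modelling choice. The overlap is disclosed one paragraph earlier, and treating the waves as separate samples may simply mean a pooled repeated cross-section of all respondents, in contrast to the matched cohort. That reading is reasonable and the estimator can stay. It does not rescue the word "independent", which is an assumption about variance and is untrue for repeat respondents.

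A second defence is that standard-error detail belongs in the SAP, and that clinic-robust errors, already named for the cohort model, would largely cure the problem. The simulation supports the second half of this for staff who do not change clinic. But the protocol does not leave the matter open: it states an independence rule, and an SAP that follows it inherits the error.

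Three further points stand and limit the weight of the finding:

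- With stable exposure groups the error is conservative. It costs power and does not create false positives.
- The all-switch figures are an algebraic limit. Nothing in the protocol suggests that every repeat respondent changes group.
- The effect could be small. With f = 0.2, r = 0.3 and no switching, v = 0.94, the standard error is about 3% too wide, the size is 0.043 and power is about 78%.

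Dependence within clinics, which the calculation leaves out, could also push the other way, so the net direction is not established even when groups are fixed.

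**Conclusion.** The concern holds, as a minor point. The independence assumption contradicts the protocol's own design, and standard errors, intervals and p-values computed under it are in general incorrect.

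If repeat staff keep their group, overlap is 30-70% and correlation is 0.4-0.6, the loss is between 4 and 21 percentage points of power from a correct 80% (80 − 76 and 80 − 59). If half switch there is no error, and beyond that the test becomes too liberal. These sizes rest entirely on assumed overlap, correlation and switching, with clinic effects set aside.

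The reach is narrow. Only the staff-experience items are affected, and they are not among the ten outcomes in the Summary of outcome measures. Job satisfaction and intention to stay (items 9 and 10) are assigned to the cohort analysis. No patient outcome is touched.

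**What to change.** Delete the statement that the two waves are treated as independent samples. Keep the pooled, nonresponse-weighted difference-in-differences regression on all respondents from both waves, and state that standard errors are clustered on staff member and on clinic. Clinic alone is enough if staff do not change clinic. Add a small-sample correction if clinics are few.

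The cost is one sentence and one standard-error option. The link between a person's two responses and the clinic identifiers are already needed for the cohort analysis, and no respondent is lost. The only downside is that intervals may become somewhat wider or narrower.
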